9.6.5 Tuberculosis and TB risk factor assessment and management

All subjects will be assessed for TB at prior to administration of IMP in PA0009 and at the time points specified in the schedule of study assessments ([Table 5–1](#)) through physical examination for signs and symptoms of TB, laboratory testing ([Section 9.6.5.1](#)), and subject questionnaire ([Section 9.6.5.2](#)).

Prior to administration of IMP, subjects will have an IGRA test (QuantiFERON TB Test is recommended) and examination for signs and symptoms of TB unless an IGRA negative result is available less than 6 weeks prior to the first dose of open-label bimekizumab. In addition, each subject will complete a TB questionnaire with questions directed at symptoms of TB and potential exposure to TB.

Test Conversion

Tuberculosis test conversion is defined as a positive IGRA result for the current test, when previous IGRA test results were negative. All subjects with TB test conversion must immediately stop IMP administration. In case of a TB test conversion, the subject must be considered as having either a suspected new latent or an active TB infection and be promptly referred to an appropriate specialist (eg, pulmonologist, infectious disease specialist) for further evaluation. If test conversion indicates LTB infection, active TB, or nontuberculous mycobacteria (NTMB) then, per UCB TB working instructions, TB test conversion (confirmed) should be classified adequately, either as due to LTB infection, active TB infection, or NTMB, respectively. Additional assessments (eg, blood tests or IGRA, chest x-rays, or other imaging) should be performed where medically relevant and documented. Such conversions should be reported to the UCB PS function.

Latent TB

In case the evaluation by the appropriate specialist indicates a new LTB infection during the study, a prophylactic TB treatment should be initiated, and the IMP can be continued no sooner

than 4 weeks after start of prophylactic TB treatment, if it is deemed likely by the Investigator that prophylactic TB treatment is continued to completion.

If prophylaxis is not initiated, the subject must be withdrawn.

Every related action should be discussed in advance with the Medical Monitor.

Once withdrawn from study treatment, subjects should return for the ET Visit, complete all ET Visit assessments, and complete a SFU Visit (20 weeks after the last dose of IMP).

Active TB or NTMB infection

Subjects who develop active TB or NTMB infection during the study must be withdrawn from the study. The subject must be immediately discontinued from IMP and an ET Visit must be scheduled as soon as possible, but no later than the next scheduled visit. The subject should be encouraged to keep the SFU Visit as specified by the protocol. Treatment should be started immediately.

Note that subjects with history of NTMB or active NTMB infection are excluded from the study regardless of prior or current therapy for this condition.

9.6.5.1 Tuberculosis assessment by IGRA

During conduct of the study, the TB assessment by IGRA (QuantiFERON TB Test is recommended) will be performed at study entry (unless an IGRA negative result is available less than 4 weeks prior to the first dose of open-label bimekizumab) and should be repeated at Week 48, Week 96, and SFU Visits for all subjects. The test results will be reported as positive, negative, or indeterminate. UCB also recommends that a TB specialist be consulted where TB (latent or active) is suspected or if there are doubts regarding test results. If latent or active TB is identified, subject must undergo appropriate study-specified withdrawal procedures.

9.6.5.2 Tuberculosis questionnaire

The questionnaire “Evaluation of signs and symptoms of tuberculosis” should be used as a source document. The questionnaire will be completed at PA0009 entry, every 12 weeks throughout the study, at Week 104, and at the SFU Visit (Table 5–1). The questionnaire will assist with the identification of subjects who may require therapy for TB. A “Yes” response to any of the questions during the study should trigger further assessments to determine if the subject has either LTB or active TB infection.

Subjects with a confirmed latent TB (where no prophylactic treatment is initiated) or active TB infection must be withdrawn from the study (as further detailed in Section 9.6.5).

9.6.5.3 Tuberculosis management

LTB infection and active TB identified during study

During the study, subjects who develop evidence of LTB infection or active TB must immediately stop further administration of IMP and will be referred to an appropriate TB specialist (pulmonologist or infectious disease specialist) for further evaluation. Evidence of LTB infection is defined as subject’s IGRA test converts to positive or indeterminate (and confirmed indeterminate on repeat), or the subject’s questionnaire or history and physical indicates that TB infection or exposure may have occurred. Evidence of active TB includes, in addition to the aforementioned tests, signs, and symptoms of organ involvement. In either

situation, the subject should be carefully assessed by a TB specialist for active TB. Subjects diagnosed with active TB or LTB infection should be withdrawn from the study and receive appropriate TB or prophylaxis therapy.

If a TB specialist excludes an active TB infection the subject can proceed with the IMP no earlier than 4 weeks after the start of an appropriate prophylactic therapy.

Any presumptive diagnosis or diagnosis of a TB infection is a reportable event. Confirmed active TB must be reported as an SAE. The Investigator is to complete and submit the TB follow-up form provided.

The subject should be transferred to the care of his/her physician and managed according to the best available standard of care. Subjects identified as having converted to active TB during the study must be withdrawn and scheduled to return for the ET Visit as soon as possible, but no later than the next scheduled study visit and complete all ET Visit assessments.

The subject should be encouraged to complete a SFU Visit (20 weeks after the last dose of IMP).

If infection with NTMB is identified during the study, the same procedure as for active TB acquired during the study must be followed.

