6.3 Withdrawal criteria

Subjects are free to withdraw from the study at any time, without prejudice to their continued care.

Subjects should be withdrawn from the study and will be asked to complete the Early Termination (ET) Visit and SFU Visit (20 weeks after the last received dose) if any of the following events occur:

1. Subject withdraws his/her consent.
2. There is confirmation of a pregnancy in a female subject during the study, as evidenced by a positive pregnancy test.
3. The Sponsor or a regulatory agency requests withdrawal of the subject.
4. Subject develops an illness that in the opinion of the Investigator would interfere with his/her continued participation, if the risk of continuing participation outweighs the potential benefit.
5. Subject develops erythrodermic, guttate, or generalized pustular form of PSO.
6. Subjects considered to have either a suspected new latent tuberculosis (LTB) infection or who develops an active tuberculosis (TB) or nontuberculosis mycobacterium infection during the study (including but not limited to, conversion demonstrated by interferon-gamma release assay (IGRA) or other diagnostic means) must be immediately discontinued from study medication and an unscheduled visit must be conducted as soon as possible, but not later than the next regular visit.

The subject must be permanently withdrawn if further examinations result in a diagnosis of active TB, or if the subject is diagnosed with LTB infection with no initiation of prophylactic treatment, prematurely discontinues prophylactic treatment, or, in the opinion of the Investigator or Sponsor, is noncompliant with prophylactic TB therapy.

Confirmed active TB is an SAE and must be captured on an SAE Report form and provided to the Sponsor in accordance with SAE reporting requirements. As with all SAEs, periodic follow-up reports should be completed as per protocol requirements until such time as the TB infection resolves.

7. Subject is noncompliant with the study procedures or medications that may present a risk to the safety of the subject in the opinion of the Investigator.
8. Subject uses prohibited concomitant medications as defined in [Section 7.8.2](#) that may present a risk to the safety of the subject in the opinion of the Investigator and/or the Medical Monitor.

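### Protocol Section 9.6.5.3 withdraws subjects diagnosed with latent TB, while its next paragraph and Section 9.6.5 let the same subjects resume study drug on prophylaxis

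*Protocol*

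**What the plan says.** Five places in the protocol deal with what happens to a subject found to have LTB.

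- **Section 9.6.5.3** says "Subjects diagnosed with active TB or LTB infection should be withdrawn from the study", and pairs this with giving TB treatment or prophylaxis. The next paragraph says that, where a specialist rules out active disease, "the subject can proceed with the IMP no earlier than 4 weeks after the start of an appropriate prophylactic therapy".
- **Section 9.6.5, under Latent TB**, says that when the specialist finds a new LTB infection, "a prophylactic TB treatment should be initiated, and the IMP can be continued no sooner" than 4 weeks after prophylaxis starts, if the investigator expects it to be completed. It adds: "If prophylaxis is not initiated, the subject must be withdrawn".
- **Section 9.6.5.2** requires withdrawal for active TB, and for confirmed LTB where no prophylaxis is started. It refers to Section 9.6.5 for detail.
- **Section 6.3, criterion 6**, requires study drug to be stopped immediately on suspicion of new LTB. Permanent withdrawal then follows "if the subject is diagnosed with LTB infection with no initiation of prophylactic treatment", or if prophylaxis is ended early or not complied with.
- **Section 9.6.5.1** says: "If latent or active TB is identified, subject must undergo appropriate study-specified withdrawal procedures". It does not mention prophylaxis.

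**The concern.** The two statements in Section 9.6.5.3 stand next to each other and overlap. A subject with diagnosed LTB, active TB excluded and prophylaxis started meets the condition of both. One ends participation; the other allows dosing to resume. Two sites could each follow the protocol's words and do opposite things with the same patient.

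This is an instruction on handling a safety event in a study whose primary objective is long-term safety. It also feeds into the analysis:

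- SAP Section 2.2.1.2 measures the secondary safety variable by TEAEs that lead to study discontinuation or permanent withdrawal of study drug. Where the TB finding is recorded as a TEAE, the sentence the site followed can decide whether it is counted.
- SAP Section 5.1 tabulates study and treatment discontinuations with their reasons.
- SAP Section 4.2.1 counts subjects who have left the study as nonresponders for ACR, PASI and MDA at later visits.

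**Working it through.** The plan gives no figure to reproduce, so the check is a comparison of the current text (not the amendment log), followed by a count of the doses that depend on the answer.

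**Step 1. One subject, five sections.** Take a subject with a specialist's diagnosis of new LTB, active TB excluded, prophylaxis started and expected to be completed.

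| Protocol section | Withdrawal from study? | Return to study drug? |
|---|---|---|
| 9.6.5.3, first statement | Yes, no exception given | Not compatible |
| 9.6.5.3, next paragraph | Not mentioned | Yes, after the 4-week minimum |
| 9.6.5, Latent TB | Only if prophylaxis is not started | Yes, after the 4-week minimum |
| 9.6.5.2 | Only if prophylaxis is not started | Silent |
| 6.3, criterion 6 | Permanent withdrawal only if prophylaxis is not started, is stopped early or is not complied with | Immediate stop; silent on restarting |
| 9.6.5.1 | Refers to withdrawal procedures, without qualification | Silent |

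The direct conflict is between the first row and rows two to four. The last two rows are less clear. Criterion 6 sits under a general lead-in that subjects should be withdrawn, and only its second paragraph makes permanent withdrawal conditional. Section 9.6.5.1 can be read as pointing to rules stated elsewhere.

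**Step 2. Is the length of the wait in dispute?** No. The minimum is 4 weeks in both places that state it. The conflict is withdrawal against continuation.

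**Step 3. Is the immediate action in dispute?** No. Sections 6.3, 9.6.5 and 9.6.5.3 all stop study drug at once and have the subject evaluated.

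**Step 4. When does the answer affect dosing?** Inputs: dosing every 4 weeks from entry to Week 100 (Protocol Table 5-1; SAP Section 7 gives 26 expected doses); IGRA repeated at Weeks 48, 96 and SFU (Section 9.6.5.1); SFU 20 weeks after the last dose; drug given after that visit's assessments (Section 8.5).

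- Total doses: 100/4 + 1 = 26, matching SAP Section 7.
- Given up to and including Week 48: 48/4 + 1 = 13. Still to come: 26 − 13 = 13, less those missed during the wait.
- Given up to and including Week 96: 96/4 + 1 = 25. Still to come: 26 − 25 = 1, the Week 100 dose. With a wait of at least 4 weeks, at most that dose is in question.
- At SFU, for completers: 26 − 26 = 0.

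Among the scheduled on-study IGRA tests, the conflict therefore matters essentially at Week 48. It also matters for cases raised earlier or by the questionnaire, which Section 9.6.5.2 schedules every 12 weeks.

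**The case against.** **The continuation paragraph may cover only suspected LTB.** It does not name LTB, so one could confine it to subjects with evidence of infection but no diagnosis. Section 9.6.5 applies the same 4-week rule to a new LTB infection found by the specialist, so this reading only moves the conflict to Section 9.6.5 against Section 9.6.5.3.

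**The withdrawal sentence uses should, where Sections 9.6.5 and 9.6.5.2 use must.** Section 6.3 introduces its own list of withdrawal criteria with should, so the word does not make withdrawal optional.

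**There are safeguards.** Section 9.6.5 requires LTB actions to be discussed in advance with the Medical Monitor, and Section 6.3 asks for contact before a withdrawal whenever possible. Section 9.6.5 also refers to sponsor TB working instructions that are not in the documents. This stands in part. A reader might infer that sites cannot manage these cases consistently or safely; the documents do not support that, given the agreed first step and the required consultation. The consultation does not say which sentence prevails.

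**Other sections might seem to take sides more firmly than they do.** A reader might take Section 9.6.5.1 as a second outright withdrawal rule, or Sections 6.3 and 9.6.5.2 as express permission to continue. Neither holds. The first can be read as deferring to the other sections; the other two limit when withdrawal is required and say nothing about restarting. Express permission appears only in Section 9.6.5 and the later paragraph of Section 9.6.5.3.

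**The analysis consequences are limited.** This stands. The study is descriptive with no formal sample size, and no test depends on these cases. SAP Section 3.4 lists withdrawal-criteria deviations as a type but leaves the criteria to a separate document, so whether a given path would be a deviation cannot be judged.

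**Conclusion.** The inconsistency is real and sits in current protocol text. For a subject with diagnosed LTB, active TB excluded and prophylaxis started, Section 9.6.5.3 calls for withdrawal, while its next paragraph and Section 9.6.5 allow study drug to resume and Section 9.6.5.2 does not require withdrawal. Sections 6.3 and 9.6.5.1 are not in direct contradiction but need to be brought into line.

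The conflict concerns disposition after the drug has been stopped. It bears mainly on Week 48 conversions and on earlier or questionnaire-triggered cases. It involves at most one dose for Week 96 conversions and has no effect on dosing for completers at SFU.

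The number of subjects cannot be derived. A reader might apply a guessed conversion rate to 200 subjects; 1% to 3%, for instance, would give 2 to 6. The documents support neither part of that sum: they give no rate, 200 is a ceiling on enrolment, and conversions at SFU, and nearly all the effect at Week 96, would have to come out. The number is probably small.

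Each such case can still change the discontinuation counts, nonresponder status at later visits and, if the event is recorded as a TEAE, withdrawal due to TEAEs. That justifies correcting the text. It does not put the study's conclusions in doubt.

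**What to change.** Reconcile Protocol Sections 6.3 (criterion 6), 9.6.5, 9.6.5.1, 9.6.5.2 and 9.6.5.3 so that one rule for latent TB appears in all of them. Section 6.3 should make clear how the immediate stop relates to permanent withdrawal, and Section 9.6.5.1 should either cite the governing section or repeat the rule. Which rule is kept is a clinical decision for the sponsor, and none is proposed here.

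The cost is a wording change at the next amendment or a clarification letter to sites. No new data collection or change to the SAP's methods is needed.

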9.6.6 Pregnancy testing

A urine pregnancy test will be performed at any scheduled or unscheduled visit if there is suspicion of pregnancy and will be confirmed with a serum pregnancy test if the urine test is positive.

Pregnancy test results must be negative prior to administering IMP.

9.6.7 Assessment of suicidal ideation and behavior

Suicidal ideation and behavior will be assessed by trained study personnel using the eC-SSRS. This scale will be used to assess suicidal ideation and behavior that may occur during the study. The visits at which the eC-SSRS assessments will be performed are specified in the schedule of study assessments (Table 5-1).

The eC-SSRS is a standardized and validated instrument developed for the assessment of the severity and frequency of suicidal ideation and behavior (Posner et al, 2011; Mundt et al, 2010). Subjects respond to standardized clinical questions that are presented in a uniform fashion. The eC-SSRS defines 5 subtypes of suicidal ideation and behavior in addition to self-injurious behavior with no suicidal intent. The eC-SSRS takes approximately 3 to 10 minutes to complete.

10 ASSESSMENT OF EFFICACY

Several assessments must be completed in order to determine the ACR response. These include the TJC and SJC based on 78 and 76 joints, respectively, PGADA, PhGADA, PtAAP, HAQ-DI, and CRP. The methods for the component measures will be described first, followed by ACR response and assessments used in secondary and other efficacy variables.

The timing for all assessments is specified in the schedule of study assessments (Table 5-1).

10.1 78/76 joint evaluation for ACR response

The Principal Investigator, another delegated physician, or an appropriately qualified medical professional (based on local requirements) who has had documented training on how to perform

these assessments correctly assesses the following joints for tenderness: the distal interphalangeal, proximal interphalangeal and metacarpophalangeal joints of the hands, and metatarsophalangeal joints of the feet, the carpometacarpal and wrist joints (counted separately), the elbows, shoulders, acromioclavicular, sternoclavicular, hip, knee, talo-tibial, and midtarsal joints. All of these except for the hips are assessed for swelling.

Artificial and ankylosed joints, as well as missing joints (ie, amputated joints), are excluded from both tenderness and swelling assessments.

One dactylitic digit is to be counted as 1 swollen joint (instead of counting as 3 in the finger or 2 in the toe).

Table 10–1 summarizes the swelling and tenderness grading criteria.

Table 10–1: Swelling and tenderness grading

Grade	Swelling response (76)	Tenderness response (78)
0	None	Not tender
1	Detectable synovial thickening	Tenderness present

10.2 28 joint evaluation for determination of DAS28(CRP)

The following 28 joints will be used for calculation of the DAS28(CRP).

- Upper extremity (26)-bilateral shoulders, elbows, wrists (includes radiocarpal, and carpal and carpometacarpal bones considered as a single unit), metacarpophalangeal (MCP) I, II, III, IV, and V, thumb interphalangeals (IP), proximal interphalangeal (PIP) II, III, IV, and V
- Lower extremity (2)-knees

10.3 Patient’s Global Assessment of Disease Activity

Subjects will score their Global Assessment of Disease Activity using a visual analog scale (VAS) where 0 is “very good, no symptoms” and 100 is “very poor, severe symptoms”.

The subject should be asked to consider both joint and skin components in their response to this question.

10.4 Physician’s Global Assessment of Disease Activity

The Investigator will assess the overall status of the subject with respect to their PsA signs and symptoms and functional capacity (considering both joint and skin components) using a VAS where 0 is “very good, asymptomatic and no limitation of normal activities” and 100 is “very poor, very severe symptoms which are intolerable and inability to carry out all normal activities”.

This assessment by the Investigator should be made blind to the PGADA.

10.5 Patient’s Assessment of Arthritis Pain

The Patient’s Assessment of Arthritis Pain VAS or ‘Pain VAS’ is part of the ACR core set of measures in arthritis (Felson et al, 1993). Subjects will assess their arthritis pain using a VAS where 0 is “no pain” and 100 is “most severe pain”.

10.6 Health Assessment Questionnaire-Disability Index score

The HAQ-DI contains 20 items divided into 8 domains that measure: dressing and grooming, arising, eating, walking, hygiene, reach, grip, and common daily activities. Subjects are required to indicate the degree of difficulty they have experienced in each domain in the past week on a 4-point scale that ranges from 0 (without difficulty) to 3 (unable to do). Any individual score of less than 2 is adjusted to 2 if the activity requires assistance from another individual or the use of an assistive device. The highest score in each category is then summed (0 to 24) and divided by the number of categories scored to give a score that ranges from 0 to 3.

10.7 CRP levels

C-reactive protein levels will be analyzed by the central laboratory.

10.8 ACR20, ACR50, and ACR70 response

The ACR20, ACR50, and ACR70 response rates are based on a 20%, 50%, and 70% or greater improvement relative to Baseline of PA0008 in the following measures:

- TJC based on 78 joints
- SJC based on 76 joints
- 3 of the 5 remaining core set measures:
 - PGADA
 - PhGADA
 - PtAAP
 - HAQ-DI
 - CRP

10.9 BSA-PSO

The BSA palm method will be used for the evaluation of BSA affected by PSO as follows:

The subject's hand, including the palm, fingers and thumb, is used as the reference point for measuring how much of their skin is affected by PSO, representing roughly 1% of the body's surface.

- Subject's palm=1%
- Head and neck=10% (10 palms)
- Upper extremities=20 % (20 palms)
- Trunk=30% (30 palms)
- Lower extremities=40 % (40 palms)

Total BSA=100%

10.10 Psoriasis Area and Severity Index (PASI)

Psoriasis Area and Severity Index will be assessed in all subjects with study entry BSA affected by PSO $\geq 3\%$ at Baseline of PA0008 determined by the method described in Section 10.9 (ie, the BSA palm method).

The PASI is the most commonly used and validated assessment for grading the severity of PSO in clinical studies (Feldman, 2004). The PASI quantifies the severity and extent of the disease and weighs these with the percentage of BSA involvement.

The percent area of involvement (BSA%) is estimated across 4 body areas; head, upper limbs, trunk, and lower limbs and then transferred into a grade (Table 10–2).

The Investigator assesses the average redness, thickness, and scaliness of lesions in each body area (each on a 5-point scale); 0=none, 1=slight, 2=moderate, 3=marked, and 4=very marked.

The PASI score ranges from 0 to 72 with a higher score indicating increased disease severity.

Table 10–2: Body areas for calculation of percent BSA for PASI

Body area	Details of area	BSA	Degree of involvement of body area ^a
Head	Face, back of head	10%	0 to 6
Upper limbs	Left, right, upper lower, flexor surface, extensor surface	20%	0 to 6
Trunk	Front, back, groin	30%	0 to 6
Lower limbs	Left, right, upper lower, flexor surface, extensor surface, including buttocks	40%	0 to 6
Total		100%	

BSA=body surface area; PASI=Psoriasis Area and Severity Index

^a Where 0=none; 1=1% to <10% affected, 2=10% to <30% affected, 3=30% to <50% affected, 4=50% to <70% affected, 5=70% to <90% affected, 6=90% to 100% affected

The PASI75, PASI90, and PASI100 responses are based on at least 75%, 90%, and 100% improvement in the PASI score compared to Baseline in PA0008. Thereafter PASI will be analyzed for the purposes of determining response only in subjects with PSO involving at least 3% of BSA at Baseline of PA0008.

